RPVi reflects measurements of ventilation induced respiratory changes in Pi over a period of time and is calculated as follows:

$$PVi \text{ or } RPVi = [(Pimax - Pimin)/Pimax] \times 100(%)$$

Multiple studies have demonstrated that PVi can predict fluid responsiveness in mechanically ventilated patients (Desebbe 2010) and can be used to optimize intraoperative fluid therapy (Desebbe 2008). Yin and Ho (2012) and Sandroni (2012) have provided meta-analyses confirming the clinical utility of PVi to guide clinical care. Among the available dynamic monitors of cardiac function in common clinical use (pulse pressure variation PPV, stroke volume variation SVV, corrected esophageal Doppler flow time FTc, etc.) the respiratory variations in the pulse oximeter plethysmographic waveform amplitude (pleth variability index PVi) has the advantage of being completely non-invasive.

The sensitivity of a dynamic monitor of cardiac function is dependent on the magnitude of the swings in the intrathoracic pressure associated with mechanical ventilation. During the introduction of these monitors into daily anesthetic management there has been a concurrent evolution in our intra-operative ventilator management protocols. During the past decade of practice, commonly recommended intraoperative tidal volumes have declined from 10 ml/kg to 8 ml/kg and now down to 6 ml/kg. Recommendations for the use of dynamic monitors as a guide for intraoperative fluid management stress that positive studies were done with controlled tidal volumes of 8 ml/kg and their sensitivity has not been established under conditions

including smaller tidal volumes. There is a pressing need to re-evaluate the performance and utility of these monitors under currently recommended respiratory management practices.

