2 STUDY OBJECTIVES

2.1 Primary Objective

This is a prospective, nonrandomized, sequential data collection study to evaluate the ability of RPVi to predict fluid responsiveness in comparison with other dynamic parameters including SVV and/or PPV. Although this is a non-interventional study, focused on data collection, patients will be assigned to one of the two study groups with different tidal volumes: 6 ml/kg IBW and 8 ml/kg IBW. The research data will not be used to modify the subject's standard of care.

Specific aims:

- Evaluate the clinical utility of the RPVi as a predictor of fluid responsiveness in mechanically ventilated patients at two specific tidal volumes (6 ml/kg IBW and 8 ml/kg IBW).
- Characterize the correlations between the RPVi and PPV and/or SVV, as measured by FDA cleared comparator systems, as predictors of fluid responsiveness at two specific tidal volumes (6 ml/kg IBW and 8 ml/kg IBW).

Hypothesis (constructed as the null):

- RPVi as a dynamic monitor of cardiac function will not predict a subsequent increase in cardiac output following the administration of a fluid bolus of a crystalloid solution at a tidal volume of either 6 or 8 ml/kg IBW in intubated, mechanically ventilated patients.

- Changes in RPVi will not differ from concurrent changes in PPV and/or SVV, as measured by FDA cleared comparator systems following the administration of a fluid bolus of a crystalloid solution at a tidal volume of either 6 or 8 ml/kg IBW in intubated, mechanically ventilated patients.

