7 STUDY PROCEDURES

- Patients are assigned to be ventilated in a volume controlled mode with a tidal volume of either 6 or 8 $\text{ml} \cdot \text{kg}^{-1}$ of ideal body weight (Devine formula) at a frequency [REDACTED]. Positive end-expiratory pressure is to be set [REDACTED] according to the attending physician.
- Anesthesia is induced as per standard of care. Radial and pulmonary arterial catheters inserted as per standard of care.
- All required sensors are placed as per the corresponding instructions for use for the various measurements
- All patients are to be studied [REDACTED] with no changes in anaesthetic protocol and no volume expansion. Unless clinically contraindicated, patients will receive an intravenous volume expansion consisting of [REDACTED] given over [REDACTED].
- Baseline set of haemodynamic measurements (stroke volume and or cardiac output) are to be performed prior to the intravenous volume expansion.
- A repeat set of hemodynamic measurements are to be performed [REDACTED] after volume expansion.

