8 STATISTICAL PLAN

Prior studies of the predictive abilities of dynamic monitors of cardiac function with respect to cardiac output have established that sample sizes of 50 patients are sufficient to characterize the performance of the monitor. However, based on an ongoing Masimo study at another clinical test site, preliminary data received suggests that, of the first 83 subjects enrolled approximately 29% were responders. Therefore, in order to analyze the ability of RPVi, the sample size will be increased to a total of up to 150 patients. The first group of up to 100 subjects will be used to gather data to determine the thresholds for fluid responsiveness that would be used for the second group of 50 subjects. The second group will be the validation set to be used to evaluate study objectives in **section 2.1**. As such, the study will be registered on ClinicalTrials.gov but only results from the validation phase will be posted.

Normality of distribution will be tested before any statistical evaluation by using the Kolmogorov- Smirnov method. Descriptive statistical data will be reported as mean \pm SD. Except for the bias between both methods (RPVi vs PPV/SVV and SV/CO measurements). Comparisons between PPV/SVV and RPVi and between CO/SV measurements will be performed with a paired student t test. PPV/SVV and RPVi as well as SV/CO measurements will be compared using Bland and Altman. In order to evaluate the ability of RPVi to reliably detect changes in PPV/SVV and for CO measurements to accurately track Flotrac CO changes we will use a method based on polar plotting of PPV/SVV and RPVi and CO measurements changes over consecutive cycles as described by Critchley et al. We will exclude from this analysis small changes of mean value of

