PPV/SVV and RPVi and CO measurements less than 3%. In this method, a good trending ability requires an angular bias no greater than ± 5 degrees and a SD for the polar angle of less than ± 15 degrees. In this method, simultaneous changes of each indices of consecutive validated respiratory cycle will be reported on a polar plot. The polar angle will be derived from the ratio of the changes of the two indices such a ratio close to one led to a null angle with the x axis, this angle approach a 90 degrees angle when the ratio diverges from one. The radius will be the mean of the simultaneous changes of the two indices between two consecutive validated respiratory cycles. In these conditions a mean angle and its SD can be calculated.

The strength of linear dependence between PPV/SVV and RPVi and SV/CO measurements for all patients will be measured by the Pearson coefficient of correlation. The mean of correlation coefficients and comparison between correlation coefficients will be performed after a Fischer's transformation. In order to analyze the ability of RPVi to correctly classify the respiratory cycle as responder or non-responder after a volume loading in respect to a theoretical threshold value of PPV/SVV of 12%, we will measure the area under the curve of a Receiver Operating Characteristic (ROC) curve. Then the selected value of RPVi for each patient will be the one which maximized the Youden index (sensitivity + (specificity - 1)). The agreement between the two classifications will be quantified by the Kappa score for each patient, taking as threshold value of RPVi the individual value determined by the ROC curve. The reported mean values of areas under ROC curves and Kappa scores will be therefore calculated from the individual values. Taking the intra patients coefficient of correlation as a dependent variable, we will estimate its relationship with potentially explanatory variables by using univariate analysis, including Student t test for qualitative data and correlation for quantitative data and multivariate analysis by multiple linear regression. Categorical binary variable will be transformed into dummy variables. Other correlations will be evaluated by Pearson coefficient.

For all comparisons, a P value < 0.05 will be considered significant. Statistical analysis will be performed using SPSS software version 13.0 for Windows (SPSS Inc., Chicago, IL).

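### Within-patient correlation between RPVi and PPV/SVV depends on the spread of PPV/SVV, so a difference in r between tidal volumes can appear without any change in RPVi error

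*Combined protocol and SAP*

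**What the plan says.** Section 8 of the combined protocol and SAP measures linear dependence between RPVi and PPV/SVV by Pearson's coefficient and then uses the coefficients in two ways.

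- They are pooled and contrasted: "The mean of correlation coefficients and comparison between correlation coefficients will be performed after a Fischer's transformation".
- They become an outcome: "Taking the intra patients coefficient of correlation as a dependent variable, we will estimate its relationship with potentially explanatory variables". The tools are t tests, simple correlations and multiple linear regression. The explanatory variables are not listed, and Fisher's transformation is not mentioned for this step.

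Section 2.1 makes the correlation a stated aim, "Characterize the correlations between the RPVi and PPV and/or SVV", at 6 and 8 ml/kg IBW. Section 7 assigns patients to one of those two volumes. Section 1.1 links ventilation to signal size: "The sensitivity of a dynamic monitor of cardiac function is dependent on the magnitude of the swings in the intrathoracic pressure". It also mentions evidence that PPV and SVV are less useful at lower tidal volumes.

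Correlation is not the only measure. Section 8 sets acceptance limits for a polar plot ("a good trending ability requires an angular bias no greater than ± 5 degrees", with an SD limit of 15 degrees) and adds an agreement analysis: "PPV/SVV and RPVi as well as SV/CO measurements will be compared using Bland and Altman". ROC and Kappa analyses follow. No part of section 8 reports or allows for how much PPV/SVV varied within each patient.

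**The concern.** A within-patient r mixes two things: how closely RPVi follows PPV/SVV, and how far PPV/SVV moved during the recording. A patient whose PPV/SVV hardly moves will have a low r even with a good sensor. Any variable that changes the spread can therefore look like a determinant of RPVi performance. Tidal volume, the one factor the study assigns, is a plausible example. Fisher's transformation does not help, because it changes the scale of r and not its dependence on spread.

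At stake is the reading of aim 2. A lower mean r at 6 ml/kg could be taken as poorer tracking by RPVi when it reflects only a narrower range of the comparator.

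**Working it through.** **The plan's own figure.** There is none to reproduce. The documents give no SD, error, expected correlation or power for this analysis, no allocation ratio between tidal volumes and no number of cycles per patient.

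**Inputs from the documents.** Two tidal volumes (section 7), a validation group of 50 (sections 4.1 and 8) and a significance level of 0.05 (section 8).

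**Assumptions.** An equal split, 25 versus 25; 60 cycles per patient; error SD e = 1.5 points in each index at both volumes; true within-patient spread s = 3.0 points at 8 ml/kg and k × 3.0 at 6 ml/kg; between-patient log-SD of spread 0.3.

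**Step 1: r for a fixed error.** With PPV/SVV = T + e1 and RPVi = T + e2, r = s²/(s² + e²).

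| k | s | r |
|---|---|---|
| 1.00 | 3.00 | 9/(9 + 2.25) = 0.80 |
| 0.90 | 2.70 | 7.29/(7.29 + 2.25) = 0.76 |
| 0.75 | 2.25 | 5.06/(5.06 + 2.25) = 0.69 |
| 0.50 | 1.50 | 2.25/(2.25 + 2.25) = 0.50 |

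**Step 2: how often a t test on Fisher z declares a tidal-volume difference** (simulated trials, same error in both groups).

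- Equal spread: about 5%.
- Spread 10% narrower at 6 ml/kg: about 20%.
- Spread 25% narrower: about 82%, or 100% if patients at the same volume do not differ in spread.
- Spread 25% narrower with error shrinking in proportion: r is unchanged and the rate is about 6%, close to nominal.

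**Step 3: other assumptions.** With errors of 1 (PPV/SVV) and 2 (RPVi), s = 3 at 8 ml/kg and 20 cycles, r falls from 0.79 to 0.68 at k = 0.75. The test rejects in 4%, 13%, 65% and 99% of runs at k = 1.0, 0.9, 0.75 and 0.6. At k = 0.75 it rejects in 44% with 10 cycles and 82% with 50.

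**Step 4: candidate error measures** (e = 1.5 in each index). Let b be the slope of RPVi on the true signal.

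- SD of RPVi minus PPV/SVV = √[(1 − b)²s² + 2e²]. At b = 1 it is √4.5 = 2.12 at any spread, and simulated rejection stays at 4% to 6%. At b = 0.7 it is √(0.81 + 4.5) = 2.30 at s = 3 and √(0.456 + 4.5) = 2.23 at s = 2.25. It then rejects in 24% of trials with unchanged error.
- The ordinary least-squares slope at b = 1 is s²/(s² + e²), so it falls from 0.80 to 0.69. It is distorted just as r is.
- The ordinary residual SD at b = 1 is √[(s² + e²) − s⁴/(s² + e²)]: √(11.25 − 7.20) = 2.01 at s = 3, √(7.31 − 3.50) = 1.95 at s = 2.25 and √(4.50 − 1.125) = 1.84 at s = 1.5. It is not spread-free. False rejection ran from 19% to 93% across scenarios.
- With the log of the within-patient SD of PPV/SVV as covariate, the tidal-volume test still rejected in 36% of trials (s = 2.25) and 77% (s = 1.5) when patients did not otherwise differ in spread. It rejected in up to 100% when error scaled with signal, a case where unadjusted z is correct.

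**Step 5: the polar plot.** Under the step 3 model, reading the 3% exclusion as 3 points, going from k = 1 to 0.75 moves the mean angle from 3.8 to 6.2 degrees and its SD from 16.7 to 17.7 degrees. The polar plot is not immune to spread either.

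**The case against.** A reader might infer that the plan decides tracking quality by correlation. It does not. The polar plot is the stated method for trending and carries the acceptance limits, while Pearson's r is offered only as the strength of linear dependence. Bland-Altman already rests on the SD of differences. This stands, and no pass/fail conclusion hangs on r. But neither method is specified by tidal volume, and neither enters the regression that seeks to explain performance.

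A reader might also infer that tidal volume is a planned explanatory variable, or that r at 6 ml/kg will be formally tested against r at 8 ml/kg. Section 8 names no variables, and neither hypothesis in section 2.1 compares coefficients between volumes. What remains is that aim 2 asks for the correlations at both volumes, and section 8 provides for comparing coefficients without saying which. A contrast is a natural reading of the results even if untested.

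The strongest objection concerns the mechanism. Section 1.1 speaks of swings in intrathoracic pressure, not of cycle-to-cycle spread of PPV/SVV within a patient, and gives no numbers. If error shrinks with the signal, there is no artefact. This also stands: the documents do not support saying that r will be falsely lower at 6 ml/kg, only that it can be. They equally give no means of telling the two cases apart, because spread and error by tidal volume are not planned outputs.

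**Conclusion.** The concern holds in conditional form. Section 8 averages, compares and models a quantity that depends on within-patient spread, and aim 2 reads that quantity at two volumes that may differ in spread. If absolute error stays fixed, a lower r at 6 ml/kg can arise with no change in RPVi error: about 20% of trials for a 10% narrower spread and about 82% for a 25% narrower one. If error shrinks in proportion to the signal, the rate is about 6%.

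These rates rest on the assumed error SD, cycle count, equal split and between-patient variation, none of which the documents supply. The analysis is secondary, and other agreement measures are planned. This is a cheap improvement that protects the reading of aim 2, not a fault that invalidates the study.

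**What to change.** In section 8:

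1. Beside mean r, report by tidal volume the within-patient SD of PPV/SVV, the within-patient slope of RPVi on PPV/SVV from a method that allows for error in PPV/SVV (with the assumed error ratio stated), and the within-patient SD of RPVi minus PPV/SVV.
2. State that the SD of differences is free of spread only if that slope is near 1.
3. Treat r and its regression as descriptive. Do not attribute a difference in r to RPVi performance unless the spread is similar or the slope and error measures point the same way.
4. List the explanatory variables for the regression, and say whether tidal volume is one.

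Two apparent remedies should not be adopted. Requiring the log SD of PPV/SVV as a covariate in every model, and using the ordinary regression residual SD as the error measure, can each produce false differences of their own (step 4 of the working).

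The cost is SAP wording and a few more table rows, with no new data. The price is a weaker claim from r.

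### Section 8 tests every comparison at 0.05 with no primary test and no rule for the two tidal volumes, so a false prediction claim could have a 7% to 18.5% chance, depending on what counts as success

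*Combined protocol and SAP*

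**What the plan says.** Section 2.1 gives two null hypotheses and ranks neither first. The first is that "RPVi as a dynamic monitor of cardiac function will not predict a subsequent increase in cardiac output" after a crystalloid bolus, "at a tidal volume of either 6 or 8 ml/kg IBW in intubated, mechanically ventilated patients". The second is that "Changes in RPVi will not differ from concurrent changes in PPV and/or SVV, as measured by FDA cleared comparator systems", again at either volume. Section 7 records "stroke volume and or cardiac output" before the bolus and repeats the haemodynamic measurements after it.

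Section 8 makes the second group of 50 subjects the validation set for the section 2.1 objectives. It then lists:

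- paired t tests, Pearson correlations and a comparison of correlations after Fisher's transformation;
- univariate and multivariable regressions on the intra-patient correlation;
- Bland-Altman and polar-plot analyses;
- an ROC area with Youden index and Kappa.

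The ROC analysis judges RPVi against a PPV/SVV threshold of 12%. The section closes with "For all comparisons, a P value < 0.05 will be considered significant". It gives no primary test, no testing order and no multiplicity adjustment, and it does not mention tidal volume.

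**The concern.** The validation phase is the confirmatory part of the study. Section 8 says that only its results will be posted, and section 10.6 mentions data needed to support a 510(k) clearance. A held-out set of 50 protects against optimism in the RPVi threshold chosen from the first group. It does not protect against choosing the tidal volume, the outcome or the test after seeing the validation data.

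Under the rule as written, any P below 0.05 counts. A result at one tidal volume, or for SV where CO fell short, could be presented as confirmation that RPVi predicts fluid responsiveness. The opening is wider because no listed test is tied to that null. The ROC analysis asks whether RPVi agrees with PPV/SVV, not whether it anticipates a rise in cardiac output.

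**Working it through.** **Inputs**

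- Level per comparison: 0.05 (section 8). Sidedness is not stated; two-sided is assumed.
- Tidal volumes: 2 (section 2.1). Each patient is assigned to one (section 7), so tests at the two volumes use different patients and are independent.
- Outcomes for the first null: CO (section 2.1), or SV and CO (sections 7 and 8), so 1 or 2.
- Correlation *r* between the SV and CO tests in the same patients: not in the documents. Assumed, and varied from 0 to 0.9.
- Responder rate: about 29%, from another study cited in section 8.
- Split of the 50 validation subjects between volumes: not given. An even 25/25 is assumed.

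**The plan's own figure.** The only figure is 0.05 per comparison; no family-wise rate or power is stated. For one test, 1 − (1 − 0.05) = 0.05, so the rule holds 5% only if there is a single test.

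**Which tests form the family.** A false claim that RPVi predicts response can come only through the first null, so the family is 2 volumes × 1 or 2 outcomes.

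**Chance of at least one false significant result.** For *k* independent tests this is 1 − 0.95^*k*. Correlated cases were simulated with 1,000,000 draws, with correlation *r* within a tidal-volume group and independence between groups.

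| What counts as success | Tests | Chance |
|---|---|---|
| Either volume, one outcome | 2 | 1 − 0.95² = 9.75% |
| Either volume, SV or CO, *r* = 0 | 4 | 1 − 0.95⁴ = 18.5% |
| Either volume, SV or CO, *r* = 0.5 | 4 | 17.3% |
| Either volume, SV or CO, *r* = 0.8 | 4 | about 15% |
| Volumes pooled, SV or CO, *r* = 0 | 2 | 9.75% |
| Volumes pooled, SV or CO, *r* = 0.9 | 2 | 7.0% |
| Both volumes, one outcome | 2, both needed | at most 5% |

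In the last row the worst case is a true effect at one volume and none at the other, which leaves a single 0.05 test.

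These rates count any P below 0.05, as section 8 does. If tests are two-sided and only the favourable direction would be claimed, both the nominal rate and the inflated rate roughly halve. For two volumes that is 2.5% against 1 − 0.975² = 4.9%, so the relative inflation stays near twofold.

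**Error rate under Holm over two volumes.** With both nulls true, 1 − 0.975² = 4.9%.

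**Power cost.** 0.29 × 25 = 7.25, so about 7 responders and 18 non-responders per volume. With a binormal model, true AUC 0.80 and a two-sided rank test, simulated power within one volume is about 68% at 0.05 and about 58% at 0.025. Two success rules follow:

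- both volumes, each at 0.05: 0.68² = 46%;
- at least one volume under Holm: 1 − (1 − 0.58)² = 82%.

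For comparison, pooling the volumes (about 14 against 36) at 0.05 gives about 95%.

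**The case against.** The strongest reply is that the 0.05 rule is not attached to prediction at all. ROC area, Youden index, Kappa, Bland-Altman and polar plots carry no stated P value. The explicit significance tests are paired t tests, comparisons of correlations and regressions, and none asks whether RPVi predicts a rise in cardiac output. This stands. It means the rates above describe what happens once a prediction test is added under the existing rule, and that the missing primary analysis is half of the problem.

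A second reply is that the split by tidal volume is inferred. Section 8 never mentions tidal volume, and its Pearson correlation is over all patients. This also stands in part. But section 8 must evaluate section 2.1, whose aims and nulls are stated at two specific volumes. Pooling lowers the rate to about 7% to 10% if both outcomes are tested; it returns to 5% only if one outcome is fixed.

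Two stronger readings are tempting, and the documents do not support them.

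- A reader might cross two volumes, two comparators and two outcomes into eight routes to success, with a much higher error rate. In section 2.1 the comparators belong to the second null and the cardiac response to the first, so they do not multiply. Rejecting the second null would say that RPVi differs from PPV/SVV, which does not favour the device.
- A reader might take "at a tidal volume of either 6 or 8 ml/kg IBW" to mean that success at one volume already rejects the null. That is a natural reading, but the text does not settle it. If both volumes must succeed on one outcome, nothing is inflated.

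Finally, the text available for review lacks the part between sections 2 and 4. The absence of a primary test is therefore confirmed only for the visible text, which includes all of section 8.

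**Conclusion.** The point holds in a conditional form. Section 8 sets a 0.05 rule for every comparison without a primary test, without a one-or-both rule for tidal volume and without fixing the outcome, and it contains no direct test of the first null. If either volume suffices, a false claim has a 9.75% chance with one outcome and about 15% to 18.5% with SV and CO. If the volumes are pooled and both outcomes are tested, it is about 7% to 10%. If both volumes must succeed on one outcome, there is no excess. The 9.75% needs only the independence of two groups of different patients; the other ranges rest on assumed within-patient correlations. The plan should be changed before validation data are seen, but the inflation is moderate and depends on a reading that the sponsor can still settle.

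**What to change.** In section 8:

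1. Name one primary test in the validation group: the AUC of pre-bolus RPVi for the cardiac-output response named in section 2.1. The responder definition should be written down before any validation data are seen.
2. State whether success requires both tidal volumes (each tested at 0.05) or either one (Holm, so the smaller p-value must be below 0.025).
3. Fix one comparator, PPV or SVV, for the head-to-head comparison.
4. Report all other comparisons with confidence intervals and no claim of significance.

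No new patients, procedures or data are needed, but the change costs more than wording. Under Holm, power within each volume is about 58% instead of 68% at a true AUC of 0.80, assuming an even split of 50 and 29% responders. On the same assumptions, requiring both volumes avoids the lower threshold but gives only about 46% power for joint success. The sponsor should make that choice openly and record it.
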